## Abbreviations

ABPM, ambulatory blood pressure monitoring

CI, clinical investigator

DXA, dual energy X-ray absorptiometry

PWA, pulse wave analysis

PWV, pulse wave velocity

HFpEF, heart failure with preserved ejection fraction

HFrEF, heart failure with reduced ejection fraction

## 1. Protocol Synopsis

**Studien ID: 01/2016/ROC-HF/KANV**

**Version: 6.0**

**Date: 07. Aug 2018**

### **Study title:**

Role of Comorbidities in Chronic Heart Failure (RoC-HF) Study

### **Study aims:**

Aims:

- To quantify the prevalence of osteoporosis in HFrEF (primary aim)
- To quantify the prevalence of vertebral fractures in HFrEF (primary aim)
- To quantify the 24-hour central blood pressure in HFrEF (secondary aim)
- To quantify arterial stiffness in HFrEF (secondary aim)

Exploratory aims:

- To elucidate the role of the bone-vascular axis in HFrEF
  - Relationship between bone metabolism and cardiac systolic function in dependence of vascular status
  - Relationship between bone metabolism and cardiac diastolic function in dependence of vascular status
- To elucidate the role of central arterial pressures and cardiac function in HFrEF
- To elucidate the relationship between arterial stiffness and cardiac stiffness in HFrEF
- To find or apply novel blood- or urine-derived biomarkers that may improve our understanding of mechanisms linking heart and bone pathologies.

### **Study design:**

Longitudinal, prospective, single-center, epidemiological cohort study.

Study procedures will be performed at the Medical University of Graz, Graz, Austria: Division of Endocrinology (DXA scans), Department of Radiology (X-ray) and Department of Cardiology (all other procedures).

Duration of active study participation: 2 x 4 hours on two separate days, follow-up visits planned as part of a separate protocol

## **Study population:**

Male or female subjects with stable chronic heart failure with reduced ejection fraction

Number of participants: 205,

### **Inclusion criteria:**

1. Age  $\geq 18$
2. NYHA class II-IV symptoms
3. Left ventricular ejection  $< 50\%$  at Visit 1
4. Treatment according to current Heart Failure Guidelines of the European Society of Cardiology
5. Willingness and ability to provide signed informed consent form (ICF) prior to participation in any study-related procedures
6. Previous diagnosis of heart failure with reduced ejection fraction defined as symptomatic left ventricular ejection fraction  $< 40\%$  requiring optimization of heart failure therapy

### **Exclusion criteria:**

1. Unplanned hospitalization within 1 month prior to the Baseline Visit.
2. Discontinuation or initiation of a pharmacologic or device treatment for HFrEF within 1 month prior to the baseline visit.
3. Coronary or peripheral revascularization procedures, valvular procedures, OR any major surgical procedure within 3 months prior to the Screening Visit.
4. Acute coronary syndrome (ACS), stroke or transient ischemic attack (TIA) within 3 months prior to the Screening Visit.
5. Any acute illness
6. Disease reducing life expectancy to  $< 1$  year, except HFrEF
7. Recipient of any organ transplant
8. Primary significant valve disease (at least moderate to severe valve disease)

## 2. Introduction

Chronic Heart failure with reduced ejection fraction (HFrEF) is a major health problem, due to high and increasing prevalence with high morbidity and mortality (1). Currently, approximately 250.000 to 300.000 people in Austria have a diagnose of heart failure, a disease with a two-year mortality that is higher than in most patients with cancer (2). Around 50% of all patients hospitalized with heart failure have a serious event within 60 days of discharge (3). Patients with HFrEF are exposed to a death rate of up to 141 deaths per 1000 patient-years. After hospitalization for heart failure reported median survival range between 1.3 and 2.4 years (4); Ninety percent of heart failure patients die from cardiovascular causes; it is, however, important to acknowledge that co-morbidities crucially contribute to disease progression (5, 6) and the number of non-cardiac co-morbidities predicts all-cause hospitalizations and even short-term mortality (6, 7).

[figure not shown]
There are many etiologies leading to HFrEF and heart failure is more often considered to be a symptom with many co-morbidities influencing the prognosis, rather than an isolated cardiac dysfunction. The most common etiology leading to HFrEF is coronary artery disease (CAD). In randomized clinical heart failure trials 68% of patients presented with ischemic cardiomyopathy (8). In Europe the ischemic cardiomyopathy is believed to be the primary etiology in 41 % of chronic heart failure patients (9). Classic Risk factors for CAD include arterial hypertension, diabetes, smoking, obesity and hypercholesterolemia. Central hemodynamic markers, such as central blood pressure, and measurements of arterial stiffness have shown independent and additive prognostic value for cardiovascular risk in the general population (10, 11), in patients with arterial hypertension (12, 13) and in patients with HFpEF (14). However this has not been shown in HFrEF patient.

The second most common reported HFrEF is dilative cardiomyopathy attributed to about 25% of chronic heart failure patients. Dilative cardiomyopathy is a descriptive term and has several underlying causes including inflammatory cardiomyopathy or toxic associated cardiomyopathy. CAD is often not present and does not significantly contribute to the progression of the disease. Arterial hypertension is thought to be risk factor for the development and progression of dilative cardiomyopathy. However little is known about the central blood pressures or arterial stiffness in this subset of patients.

HFrEF is associated with altered bone metabolism and novel evidence from our research group strongly suggests that bone metabolism interferes with cardiac function. However, the prevalence of altered bone metabolism and osteoporosis as well as the link with cardiac function has not been analyzed in patients with chronic heart failure. Given that bone metabolism in patients with HFrEF responds to hemodynamic changes (15), vascular function may play a mediating role in the bone-

heart axis. However, epidemiological studies totally lack to disentangle these complex relationships in HFrEF.

The role of bone disease in this context has attracted increasing attention. Experience of a hip fracture doubles the mortality rate in heart failure patients (16) Moreover, treatment of osteoporosis after hip fracture reduced mortality in the HORIZON trial (17). Bone strength is crucially determined by bone metabolism. The role of bone metabolism in HFrEF is, however, completely unknown.

**Figure 1: Risk for all-cause hospitalization as a function of number of non-cardiac co-morbidities in patients with heart failure (7).**

Increasing evidence suggests that bone should be regarded as an endocrine organ. Of note, novel cross-sectional data from our research group and others point towards an independent link between bone metabolism and cardiac function. Proposed mechanistic links include cardiovascular effects of bone-derived peptides that are increasingly secreted in the course of HFrEF. These include effects on blood pressure, glucose metabolism or vascular calcification which may further promote cardiac remodeling and deterioration of cardiac function. The clinical relevance of these mechanistic links for cardiovascular outcomes in HFrEF remains elusive in large parts. This is due to the fact that available longitudinal analyses are limited by their retrospective approach and, importantly, the lack of profound profiling of study participants: studies on HFrEF patients lack important baseline information on bone characteristics such as bone mineral density or prevalence of vertebral fractures. Thus, current evidence is insufficient to fully enlighten the role of disturbed bone metabolism and bone status in HFrEF. The current “Role of Co-morbidities in Heart Failure”(RoC-HF study) is therefore designed to address the question whether disturbances in bone metabolism affect cardiac function and cardiovascular outcomes in a highly standardized cohort of HFrEF patients with comprehensive assessment of bone/ mineral metabolism, fracture status and bone mineral density at baseline.

### Sample size calculation:

Based on previous epidemiological studies we expect a prevalence of osteoporosis in RoC-HF of 20 % (95% confidence interval: 14 -26). Calculating with a significance level of 5% and a two-sided P-value leads to a number of 171 participants to be analyzed. Calculating with 20% unavailable data due to invalid ABPM, missing laboratory values or other missing parameters, we will need to enroll 205 subjects in total.

## 3. Study aims

This study aims to create a large and previously unavailable database of patients with stable HFrEF with comprehensive assessment of bone, skeletal and vascular status. RoC-HF will facilitate cross-sectional and, eventually, longitudinal mechanistic epidemiological analyses to disentangle the role of the bone- vascular axis in HFrEF.

Aims:

- To quantify the prevalence of osteoporosis in HFrEF
- To quantify the 24-hour central blood pressure in HFrEF
- To quantify arterial stiffness in HFrEF

Exploratory aims:

- To elucidate the role of the bone-vascular axis in HFrEF
  - Relationship between bone metabolism and cardiac systolic function in dependence of vascular status
  - Relationship between bone metabolism and cardiac diastolic function in dependence of vascular status
- To elucidate the role of central arterial pressures and cardiac function in HFrEF
- To elucidate the relationship between arterial stiffness and cardiac stiffness in HFrEF
- To find or apply novel blood- or urine-derived biomarkers that may improve our understanding of mechanisms linking heart and bone pathologies.

## 4. Relevance

HFrEF is associated with altered bone metabolism and fractures increase mortality risk in patients with HFrEF (16). Yet, bone disease is not even listed among relevant co-morbidities in international HFrEF guidelines . Therefore, bone disease in HFrEF is underdiagnosed and undertreated.

Retrospective analyses indicate that osteoporosis as the manifestation of altered bone metabolism is present in approximately 1 of 5 patients with HFrEF (see **Table 5**). However, prospective studies lack to quantify the burden of osteoporosis in HFrEF. Given that some studies even indicated a mortality reduction by osteoporosis therapy (17) is it of critical importance to fill this gap in evidence. The RoC-HF study will prospectively determine the prevalence of osteoporosis, fractures and altered bone metabolism and the link with cardiac function in a well-standardized cohort of HFrEF patients. RoC-HF will thus provide novel and important evidence on the relevance of bone disease in HFrEF. It is the final aim of RoC-HF to establish bone disease as a relevant co-morbidity in international HFrEF guidelines and, thus, to improve medical treatment of these patients.

## 5. Study population

Male or female subjects with stable chronic heart failure with reduced ejection fraction.

Number of participants: 205

### a. Recruitment

Patients will be recruited from the Department of Cardiology or the Department of Internal Medicine and will be contacted personally.

### b. Inclusion criteria

1. Age  $\geq 18$
2. NYHA class II-IV symptoms
3. Left ventricular ejection  $< 50\%$  at Visit 1
4. Treatment according to current Heart Failure Guidelines of the European Society of Cardiology
5. Willingness and ability to provide signed informed consent form (ICF) prior to participation in any study-related procedures
6. Previous diagnosis of heart failure with reduced ejection fraction defined as symptomatic left ventricular ejection fraction  $< 40\%$  requiring optimization of heart failure therapy

### c. Exclusion criteria

1. Unplanned hospitalization within 1 month prior to the Baseline Visit.

2. Discontinuation or initiation of a pharmacologic or device treatment for HFrEF within 1 month prior to the baseline visit.
3. Coronary or peripheral revascularization procedures, valvular procedures, OR any major surgical procedure within 3 months prior to the Screening Visit.
4. Acute coronary syndrome (ACS), stroke or transient ischemic attack (TIA) within 3 months prior to the Screening Visit.
5. Any acute illness
6. Disease reducing life expectancy to < 1 year, except HFrEF
7. Recipient of any organ transplant
8. Primary significant valve disease (at least moderate to severe valve disease)

#### **d. Premature discontinuation of study participation**

Subjects may be discontinued for the following reasons:

- CI decision for any reason
- Subject Decision: The subject or the subject's designee, (e.g., parents or legal guardian), requests to be withdrawn from the study.
- The subject is lost to follow-up

## **6. Investigational Plan**

### **a. Study design**

Longitudinal, prospective, single-center, epidemiological cohort study.

Study procedures will be performed at the Medical University of Graz, Graz, Austria:

- Division of Endocrinology (DXA scan)
- Department of Radiology (X-ray)
- Department of Cardiology (all other procedures).

Duration of active study participation: 3 (+2) days, follow-up visit planned

Study duration: 2 years for cross-sectional part, follow-up planned

### **c. Study visits**

#### **Visit 1**

Visit 1 will be scheduled on the day of Screening or at a separate day. Study procedures will include the following:

1. Signing of informed consent forms (possible already during screening): General form, form of the Biobank Graz, separate form for data generation from stored samples.
2. Assessment of medical history
3. Assessment of medication history
4. Physical examination
5. ECG
6. Echocardiography
7. Spot urine pregnancy test for women of child-bearing age
8. 24-hours ambulatory blood pressure monitoring (ABPM).

9. Scheduling of visit 2, at least 2 days after visit 1 to facilitate performance of 24-hours ABPM. The patient will be advised to remove and switch off the ABPM device 24 hours after attaching. The patient will be advised to attend visit 2 as fasting and non-smoking over the preceding night.

## Visit 2

Visit 2 will take place at least 2 days after visit 1 to facilitate performance of 24-hours ABPM. Visit 2 will take place in the Clinical Studies Outpatient Clinic of the Department of Cardiology. The participant should be fasting and should not have smoked over the previous night. Following study procedures will be performed:

1. X-ray of the thoracic and lumbar spine. Women of child-bearing age will not perform X-ray in case of a positive pregnancy test during visit 1.
2. Re-obtainment of ABPM device. If ABPM was unsuccessful it can be repeated once, if the patient agrees.
3. Vital signs (office blood pressure and heart rate)
4. Hand Grip
5. 4m Gait Speed
6. Sampling of blood (65 mL) and spot urine (12 mL)

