7. PWA
8. PWV
9. Questionnaires
10. DXA-scan. Women of child-bearing age will not perform DXA in case of a positive pregnancy test during visit 1.

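### Minor safety improvement: the pregnancy test that gates the spine X-ray and DXA is done at Visit 1, but both exposures are at Visit 2, with no maximum interval and no listed same-day check

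*Combined protocol and SAP*

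**What the plan says.** **Test.** Section 6c lists the test as item 7 of Visit 1: "Spot urine pregnancy test for women of child-bearing age". It follows from a question on child-bearing potential in the medical history (Section 6d), which is also taken at Visit 1.

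**Exposures.** Both are in the Visit 2 list of Section 6c, the spine X-ray as item 1 and DXA as item 10. Each carries the same condition: "Women of child-bearing age will not perform X-ray in case of a positive pregnancy test during visit 1" and "Women of child-bearing age will not perform DXA in case of a positive pregnancy test during visit 1". The X-ray and DXA parts of Section 6d and the ethics section (Section 8) repeat it. The pregnancy test part of Section 6d also withholds both procedures on a positive result, without naming the visit at which the test is done.

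**Interval.** The Visit 2 text reads: "Visit 2 will take place at least 2 days after visit 1 to facilitate performance of 24-hours ABPM". Item 9 of Visit 1 says the same. On overall duration, the synopsis has "Duration of active study participation: 2 x 4 hours on two separate days" and Section 6a has "Duration of active study participation: 3 (+2) days, follow-up visit planned".

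**The concern.** The test exists to keep a pregnant participant away from study radiation, so it should describe her status when the exposure happens. Here it describes her status at an earlier visit. The interval has a floor but no ceiling, and the floor was chosen for the blood pressure recording, not for the validity of the test. If Visit 2 slips, no written rule calls for a new test.

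The rule also works in one direction only. A positive result blocks exposure, but nothing says that a negative result must be on file first.

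At stake is an avoidable fetal exposure in a non-interventional study whose ethics section names radiation as a safety issue and offers this test as its pregnancy safeguard.

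**Working it through.** The plan states no figure on this point that could be reproduced. The check compares the sections and needs little arithmetic.

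**1. Shortest gap.** 2 days (Section 6c, stated under both visits).

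**2. Longest gap.** No visit window is written. There are three ways to read the duration statements:
- Section 6a with Visit 1 as day 1 and Visit 2 on day 3 to 5: 3 − 1 = 2 days to 5 − 1 = 4 days.
- Section 6a with the bracketed 2 days reserved for a repeat of the ambulatory recording: 3 − 1 = 2 days. That repeat is decided at item 2 of Visit 2, after the X-ray.
- Synopsis: two separate days, with no bound on the time between them.

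The first two are inferences from a participation duration.

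**3. Does the recording fix the date of Visit 2?** No. "The patient will be advised to remove and switch off the ABPM device 24 hours after attaching". The device is only handed back at Visit 2, so a late Visit 2 would not disturb the recording.

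**4. Is there another check at Visit 2?** None is listed. The ten items include no pregnancy test or question. The X-ray comes first and the urine sample is item 6, so that sample comes too late for the X-ray. The laboratory panels in Tables 1 and 2 contain no pregnancy marker. Pregnancy is not among the exclusion criteria (Section 5c).

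**5. What the rule does with each possible test result, read literally:**

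| Visit 1 test | X-ray and DXA at Visit 2 |
|---|---|
| Positive | Barred |
| Negative | Allowed, whatever the interval |
| Not done | Not barred by the wording |

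The third row matters because the pregnancy test part of Section 6d says only that women are asked to take the test.

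**6. Is the X-ray really at Visit 2?** The ambulatory blood pressure part of Section 6d has the device attached at Visit 1 before the X-ray, which could suggest an X-ray on the Visit 1 day. Three places say otherwise: the Visit 2 list, the pregnancy test part, and the X-ray part, which makes it the first procedure of Visit 2. Visit 2 is the better reading, and the other wording is an inconsistency.

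**7. Dose.** Section 8 gives at most 1.5 mSv for the X-ray and about 0.3 mSv for DXA: 1.5 + 0.3 = 1.8 mSv. These are participant doses. No fetal dose is given.

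**8. Women affected.** The documents give neither the share of women of child-bearing age among the 205 participants nor a validity period for the urine test. Even a known share would count the women to be tested, not those whose status changes or is missed between test and exposure.

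**The case against.** The strongest reply is that the gap is short in practice. Section 6a points to a few days, and over 2 to 4 days few pregnancies would newly become detectable. Nothing in the documents makes a test of that age inadequate. Radiology may ask about pregnancy before any X-ray, and DXA follows a departmental operating procedure that was not available for this review. The investigator can also discontinue a participant for any reason (Section 5d).

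Most of this stands and explains why the point is minor. It does not remove the point. Section 6a gives a participation duration that differs from the synopsis and sets no window for Visit 2. The local checks may exist, but the protocol neither describes nor requires them.

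A reader might infer more: that long delays are planned, that women will be exposed with no check at all, or that harm to a fetus is likely. The documents support none of these. They leave the interval open without planning a long one, they are silent on local practice, and they provide no basis for sizing harm.

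**Conclusion.** The point holds as a minor, optional safety improvement. The only scheduled pregnancy test precedes both exposures by at least 2 days, no maximum interval is written, no same-day check is listed, and a negative result is not required.

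The gap is about 2 to 4 days if Section 6a reflects the intended schedule, which is an assumption, and has no written limit otherwise. The number of women who would be exposed because of the gap cannot be estimated; it is probably very small. The conclusion rests on taking Visit 2 as the time of the X-ray, and on no same-day check being required by the protocol itself. If Radiology and the DXA unit already test or ask on the day, the change would only put that practice into the protocol.

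It would be wrong to read this as a threat to the results. Estimates of osteoporosis and fracture prevalence, the planned analyses and the sample size are untouched.

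**What to change.** Move the existing spot urine test from Visit 1 to the start of Visit 2, before the X-ray, and require a negative result that day before X-ray and DXA. The child-bearing question can stay in the Visit 1 history, so that the women who need the test are known in advance.

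Text to change:
- Section 6c: move item 7 of Visit 1 to the head of the Visit 2 list, and reword the conditions on items 1 and 10 of Visit 2.
- Section 6d: reword the pregnancy test, X-ray and DXA parts.
- Section 6d, X-ray part: allow the urine test to come before the X-ray, which is now the first procedure.
- Section 6d, ambulatory blood pressure part: delete the reference to the X-ray at Visit 1.
- Section 8: reword the closing condition on X-ray and DXA.

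The cost is slight Visit 2 logistics for a few women: a urine sample before going to Radiology, and eligibility for X-ray and DXA known only that day. The number of tests does not rise.

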7. PWA
8. PWV
9. Questionnaires
10. DXA-scan. Women of child-bearing age will not perform DXA in case of a positive pregnancy test during visit 1.

### d. Study procedures

#### Blood/urine sampling – immediate determination

32mL of blood and 8mL of spot urine will be processed directly after collection for the purpose of immediate determination of parameters, at the Clinical Institute of Medical and Chemical Laboratory Diagnostics (18mL) and at the Laboratory platform of Division of Endocrinology (14mL). An oversight is provided in **Table 1** and **Table 2**.

**Table 1: Endo lab parameters from blood (14 mL).**

3mL EDTA-plasma (on ice)	8mL Serum (room temperature)
Parathyroid Hormone	TSH
Osteocalcin	fT3
FGF-23	fT4
CTX	25-hydroxy-vitamin D
	bALP
3mL EDTA-plasma (room temperature)	P1NP
Aldosterone (plasma aldosterone concentration)	P3NP
Renin (plasma renin concentration)	TRAP
	IGF-1

FGF-23, fibroblast growth factor-23; TSH, thyroid stimulating hormone; fT3, triiodothyronine; fT4, tetraiodothyronine; bALP, bone-specific alkaline phosphatase; P1NP, intact N-terminal propeptide of procollagen type 1; P3NP, amino-terminal propeptide of type III procollagen; TRAP, active isoform 5b of the tartrate-resistant acid phosphatase; IGF-1, Insulin-like growth factor 1.

